4. STUDY DESIGN

4.1 OVERALL DESIGN

An overview of the study design is provided in Section 1.2.

The study will be conducted in two parts, of which Part 1 will be in healthy participants and Part 2 will be in CHB patients (see Section 1.2). All parts of the study are Observer-blind (see Section 6.3.2). All members of the project and study team who are not in direct contact with the participants may be unblinded. Part 1 will evaluate the safety, tolerability and PK of RO7239958 following subcutaneous (SC) administration of single ascending doses in healthy participants. Part 2 will evaluate the safety, tolerability, PK, and pharmacodynamics (PD) of multiple SC doses of RO7239958 in CHB patients established on NUC therapy, and comprises two subparts, Part 2a and Part 2b. Part 2 is a dose range finding study (DRF).

Part 1 – Single-Ascending Dose (SAD) Study in Healthy Participants

In Part 1, at least four cohorts will receive a single dose of RO7239958 or placebo. An optional cohort with participants receiving RO7239958 or placebo may be included, based on the need for further safety or PK data. Ten healthy participants, eight receiving RO7239958 and two receiving placebo, will be enrolled in each cohort using a 4:1 randomisation scheme. [REDACTED]

[REDACTED] Each cohort will implement sentinel dosing to monitor acute reactions over 24 hours post-dosing. Two participants will be dosed on Day 1, and at least one of two participants will have received RO7239958; the remaining eight participants shall be dosed the following day (i.e., after 24 hours) following satisfactory clinical safety review of the first two participants by the Investigator. For each cohort, safety will be monitored for 28 days (21 days for safety assessment plus 7 days of clinical safety observation), before escalating to the next cohort. A dose escalation meeting will take place prior to starting the next cohort. In all participants, safety will be monitored for a total of 12 weeks post-dosing.

Part 2 – Dose Range Finding (DRF) Study in CHB Patients

Part 2 is a placebo-controlled, adaptive, parallel multiple-dose study in participants with CHB on stable NUC therapy, with the aim to study the safety, tolerability, PK and PD of RO7239958, and the relationship between RO7239958 PK and PD parameters. Dosing will be initiated in CHB patients with a safe dose as determined in Part 1, which will fall within the human efficacious dose range predicted with PK/PD modeling. Part 2 is divided into two parts, Part 2a and Part 2b.

Part 2a

In Part 2a, CHB patients will be enrolled into one of two arms (Arms 1 and 2), which will run in parallel. Each arm will enroll seven participants using a 6:1 randomization scheme. To ensure balance between arms, enrolment of HBeAg positive participants will be capped. Participants of each arm can receive up to five doses of RO7239958 or placebo over 4 weeks.

[REDACTED]

[REDACTED] *Two* additional, parallel arms (Arms 3 and 4) will open after Arms 1 and 2 have enrolled and followed-up for at least 28 days a sufficient number of participants to provide the safety and PK/PD information required to further inform dose and regimen optimization. *An optional Arm 5 will open if further doses or regimens need to be explored based on data from Arms 3 and 4.* A data review meeting will also take place before opening Arms 3 and 4 (*and potentially optional Arm 5*). Decision on dose levels and regimens for Arms 3 and 4 will be based on the safety, PK, and PD data from Arms 1 and 2 and all available safety and PK data from Part 1. If efficacious dose levels cannot be reliably predicted from PK/PD modeling and Part 1 data, the doses administered in Part 2a will be within the range demonstrated to be safe and well tolerated in Part 1.

[REDACTED]

[REDACTED] In all patients, safety will be monitored for a total of 12 weeks post-dosing.

Part 2b (optional)

The two additional arms (Arms 6 and 7) of Part 2b will open if further doses or regimens need to be explored based on the data from Part 2a, or a dose or regimen from Part 2a needs to be optimized and additional data evaluated. There may be inclusion of participants who are not treated with NUCs, or inclusion of a larger number of participants of a given HBeAg status. Each arm in Part 2b will comprise seven participants randomized to RO7239958 or placebo using a 6:1 randomization scheme.

[REDACTED] In all patients, safety will be monitored for a total of 12 weeks post-dosing.

4.1.1 Length of the Study

Part 1: The total duration of the study for each participant will be up to 16 weeks, divided as follows:

- Screening: Up to 28 days
- In clinic period: Days -1 to 3.
- Treatment Period: Day 1
- Safety follow-up: up to at least 84 days after the dose of RO7239958 or placebo.

Part 2a: The total duration of the study for each participant will be up to 20 weeks divided as follows:

- Screening: Up to 28 days.

- In clinic period (optional): Days 1 to 3 and Days 29 to 30 (overnight stay optional).
- Treatment Period: Day 1 to 29.
- Safety follow-up: up to 84 days after the last dose of RO7239958 or placebo.

Part 2b: The total duration of the study for each participant will be up to 28 weeks divided as follows:

- Screening: Up to 28 days.
- In clinic period (optional): Days 1 to 3 and Days 29 to 30 (overnight stay optional).
- Treatment Period: Day 1 up to Day 85. Safety follow-up: up to 84 days after the last dose of RO7239958 or placebo.

4.1.2 Dose Escalation Decision

The decision to escalate the dose in Part 1, and the decision to open Arms 3 and 4 in Part 2a (and potentially further arm(s) in *Part 2a and* Part 2b), will be made jointly by the Sponsor study team, the Investigator, and any other person the Investigator or the Sponsor consider necessary to assist with the decision (see Section 4.1.4). In Part 1, the decision will be made prior to each RO7239958 dose escalation following review of all relevant information, including applicable AEs, ECGs, vital signs, laboratory test results, and available PK data collected at the previous dose levels as applicable.

Dosing will be initiated in CHB patients in Part 2a with a safe dose as determined in Part 1, which will fall within the human efficacious dose range predicted with PK/PD modeling. The maximum dose in Part 2 will not exceed the maximum dose tested in Part 1 under any circumstances. Part 2a will only commence once all clinically relevant data are available from Cohort 4 of Part 1. Dose levels in Arms 3 and 4 of Part 2a will be based on all available PK and safety data from Part 1, and the safety, PK, and available PD data from Arms 1 and 2. Part 2a will employ real-time data analysis obtained during dosing and follow-up post-dosing. If data from Arms 1 and 2 are supportive, Arms 3 and 4 may start to enroll participants early, while follow-up post-dosing is ongoing in Arms 1 and 2. However, Arms 3 and 4 will only open once sufficient participants in Arms 1 and 2 have completed at least 28 days of post-dosing follow-up. *Arm 5 will be optional and will open if further doses or regimens need to be explored based on data from Arms 3 and 4.*

4.1.2.1 Part 1 - Dose-Escalation Decision Criteria

Part 1 uses an adaptive dose-escalation process that may be modified if:

- Events emerge that the Sponsor and/or the Investigator consider indicators that the planned dose-escalation step would result in unacceptable risks for the safety of healthy participants.
- The Sponsor and the Investigator agree to do so, and neither considers that the proposed subsequent dose level poses an unacceptable risk to the study subjects.

Single doses will not be escalated if the dose-escalation stopping criteria are met (see Section 4.1.3).

4.1.3 Stopping Rules Criteria

Liver-related

Isolated elevations in liver transaminases (ALT or AST) in the absence of liver function abnormalities may occur after administration of RO7239958 as a recognized LNA SSO class effect. In addition to the LNA SSO class effect, CHB patients may also hypothetically experience transaminase flares if HBsAg suppression leads to immune-restoration. Stopping criteria have been developed to take these potential effects into account.

Part 1: If, at a given dose level, one or more of the criteria described below is fulfilled, dose-escalation to the next cohort will be paused in order to assess the possible underlying causes and relation to RO7239958. If a relation to study treatment cannot be excluded by the Investigator and the Sponsor's Medical Monitor, dose escalation will be halted.

Criteria:

- At least two of eight healthy participants receiving RO7239958 experience dose-limiting AEs (DLAEs) of an ALT or AST increase $> 5x$ the upper limit of normal (ULN; confirmed by retesting within 48 hours) with preserved measures of liver function (total bilirubin, and INR or prothrombin time [PT]),

or

- At least one of eight healthy participants receiving RO7239958 experiences one of the following DLAEs: confirmed (within 48 hours) increase in ALT or AST $> 3x$ ULN accompanied by confirmed total bilirubin $> 2x$ ULN, INR > 1.5 , or PT $\geq 1.5x$ ULN, or appearance of jaundice or symptoms suggestive of drug-induced liver injury (e.g., fatigue, nausea, vomiting, right upper quadrant abdominal pain or tenderness, fever, rash, and eosinophilia).

Part 2: If, at a given dose level and/or regimen, one or more of the criteria described below is fulfilled, dosing in a patient and in a given arm, and any dose escalation, will be paused in order to assess the possible underlying causes and relation to RO7239958. If a relation to study treatment cannot be excluded by the Investigator and Sponsor's Medical Monitor, dosing and any potential dose escalation will be halted.

Criteria:

- At least two of six patients receiving RO7239958 experience a DLAE of an ALT or AST increase of > 8-fold relative to the baseline value (defined as the average values of the two measurements taken within the screening period), confirmed by retesting within 48 hours, with preserved measures of liver function (total bilirubin and INR or PT),
or
- At least one of six patients receiving RO7239958 experiences one of the following DLAEs: confirmed (within 48 hours) increase in ALT or AST > 3-fold the baseline value, accompanied by confirmed total bilirubin > 2x ULN, INR > 1.5, or PT \geq 1.5x ULN, or appearance of jaundice or symptoms suggestive of drug-induced liver injury (e.g., fatigue, nausea, vomiting, right upper quadrant abdominal pain or tenderness, fever, rash, and eosinophilia).

Repeat dosing of a participant within an arm will be delayed if the participant receiving RO7239958 experiences an ALT or AST increase > 5-fold and \leq 8-fold relative to the baseline value, confirmed by retesting within 48 hours, with preserved measures of liver function (total bilirubin and INR or PT). Dosing may resume when the ALT or AST levels return to \leq 5-fold the baseline value.

Other stopping criteria

All Parts: Dosing and dose-escalation in healthy participants in Part 1 and dosing for a patient and a treatment arm and any potential dose escalation in Part 2 will not be implemented as planned if one of the criteria described below is fulfilled, unless it is apparent to the Investigator and the Sponsor that the occurrence is not related to RO7239958.

Criteria: At least two of eight healthy participants or at least two of six CHB patients receiving RO7239958 experience one or more of the following DLAEs:

- Confirmed decline in eGFR < 60 ml/min
- Grade 3 or 4, or otherwise significant (as defined by the Investigator) RO7239958-related AEs of the same character, or Grade 3 or 4 laboratory abnormalities.
- Other findings (regardless of the incidence rates) that at the joint discretion of the Sponsor and the Investigator indicate that dosing and any dose escalation should be halted (see Section 7.1).

General considerations

Part 1: In case dose-escalation is stopped, lower doses within the tolerated dose-range could be investigated or a previous dose could be repeated in subsequent cohorts, by mutual agreement between the Sponsor and Investigator, in order to increase the amount of data within the tolerated dose-range.

Part 2: In case an arm is stopped, alternative regimens within a previously tolerated dose/exposure range could be further investigated, or a previous regimen could be repeated in subsequent arms, by mutual agreement between the Sponsor and Investigator, in order to increase the amount of data within the tolerated dose/exposure range.

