4.2 SCIENTIFIC RATIONALE FOR STUDY DESIGN

The study rationale is provided in Section [2.1](#).

In order to reduce safety risks, the effects of each dose level will be reviewed carefully before escalating to the next dose level. Dose escalation will take place after a review of safety, tolerability, and available PK data, as described in Section [4.1.2](#). Stopping rules are detailed in Section [4.1.3](#). The safety observation period has been set to 21 days for the safety laboratory assessments and to 28 days for adverse event monitoring, and this approach is supported by data from the BP39405 study (RO7062931) which has completed dosing in healthy participants (see the [RO7062931 Investigator's Brochure](#)).

The DRF part of the study, Part 2a, will evaluate the safety, tolerability, PK and PD effects of multiple doses of RO7239958 in CHB patients. Part 2b is an extension part of Part 2a to evaluate alternative regimens, additional safety, PK and PD data, if required.

[REDACTED] The approach is based on the consideration that the PK profile of RO7239958 is anticipated to show minimal variation between healthy participants and patients, and that the doses in Part 2 will never exceed the maximum safe dose defined in healthy volunteers in Part 1. Opening Part 2a with two parallel dosing levels will increase the likelihood of detecting antiviral activity and identifying a dose for regimen optimization in subsequent arms, while remaining within acceptable safety margins, based upon non-clinical data and data from Part 1.

In this study RO7239958 will be given as an add-on to NUC treatment. It is envisaged that in future studies RO7239958 will contribute to combination regimens with one or more antiviral agents or immune-enhancers, with the aim of inducing a HBV cure.

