6.6 DOSAGE MODIFICATION

The decision to proceed to the next dose level of RO7239958 (either an increase or a decrease), will be made by the Study Team (and the Investigator) based on safety, tolerability and available PK and/or PD data obtained described as in Section 4.1.2.

If unacceptable adverse events, or pharmacological effects, reasonably attributable to RO7239958 in the opinion of the Investigator are observed in the participants in a cohort or an arm, dosing and any dose-escalation will be temporarily halted for maximally 3 weeks (see Section 4.1.2) and no further participants will be dosed until a full safety review of the study has taken place. Relevant reporting and discussion with the Medical Monitor, relevant site personnel (i.e., Investigator), and the IRB/IEC will take place before resumption of dosing.

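### When a lower-dose arm in Part 2a meets a liver stopping criterion, the required pause does not reach a parallel arm already open at a higher dose

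*Combined protocol and SAP*

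**What the plan says.** Section 4.1 states that "CHB patients will be enrolled into one of two arms (Arms 1 and 2), which will run in parallel", and that "Participants of each arm can receive up to five doses of RO7239958 or placebo over 4 weeks". Section 4.2 gives the reason for starting with two arms: "Opening Part 2a with two parallel dosing levels will increase the likelihood of detecting antiviral activity". The doses and regimens are redacted.

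The Part 2 liver rule in Section 4.1.3 is triggered as follows: "If, at a given dose level and/or regimen, one or more of the criteria described below is fulfilled". The criteria are at least two of six active patients with an isolated ALT or AST rise above 8-fold baseline, or at least one of six with a rise above 3-fold plus impaired liver function or suggestive symptoms. The action is that "dosing in a patient and in a given arm, and any dose escalation, will be paused" so that cause and relation can be assessed. If relation cannot then be excluded, dosing and escalation are halted; that later sentence names no arm.

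The other (non-liver) criteria in 4.1.3 carry this Part 2 action: "dosing for a patient and a treatment arm and any potential dose escalation in Part 2 will not be implemented as planned", "unless it is apparent to the Investigator and the Sponsor that the occurrence is not related to RO7239958".

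Section 6.6 has a wider action. It stops dosing of all further participants pending a study-level safety review, but its trigger is unacceptable events "reasonably attributable to RO7239958 in the opinion of the Investigator are observed in the participants in a cohort or an arm".

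**The concern.** Blocking escalation protects patients from a higher dose only while that dose is unopened. This works in Part 1, where cohorts open in sequence. In Part 2a two dosing levels are open from the start, so continuing the higher one is not an escalation. Followed as written, the rule can stop the lower dose for a possible drug-related liver signal while patients on the higher dose receive their next scheduled injection.

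This is the first repeat dosing of the compound in humans. Section 4.1.3 itself describes transaminase elevation as a recognised class effect, and Section 4.2.3 names hepatic injury as a potential risk. The synopsis states that no Internal Data Monitoring Committee is planned, so the written rule and the Sponsor/Investigator review are what decide the matter.

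**Working it through.** The plan gives no figure on this point. The check is textual, followed by two illustrations of scale.

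**1. Are two doses open at once?** Yes for Arms 1 and 2 (4.1 for parallel running, 4.2 for two dosing levels). Differing doses are not shown for any other parallel pair.

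**2. Whom does the liver pause cover?** Suppose the lower-dose arm triggers.

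| Element of the pause | Covers the open higher-dose arm? |
|---|---|
| The patient | No |
| The given arm | No, it is a different arm |
| Any dose escalation | No, its dose is already assigned and running |

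An arm at an equal dose is different: the trigger wording refers to a dose level and/or regimen and can be read as already covering it. The clear gap is the higher-dose arm.

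**3. Does any other provision require a stop during the review?**

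| Provision | Effect during the review |
|---|---|
| 4.1.3, halt if relation cannot be excluded | Possibly study-wide, but applies only after the assessment |
| 6.6 | Stops all dosing, but needs the Investigator's judgement that the event is unacceptable and reasonably attributable |
| 4.1.3, last bullet (other findings) | Joint discretion |
| 4.1.4 | Immediate Sponsor contact; prescribes no action for another arm |
| 7.1 and Section 8 | Judgement about individual participants |
| 4.1.3, other arm's own criteria and its individual ALT/AST delay | Act only once that arm's own patients are affected |
| 4.1.2, Part 1 dose cap | Limits the dose; does not pause it |

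None requires the higher-dose arm to pause solely because the lower-dose arm has met a liver criterion.

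**4. Non-liver rule.** It acts unless the event is apparently unrelated, so there is no interval of waiting for attribution. Its action still reaches only the patient, the arm and escalation. It shares the scope limit but not the timing problem.

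**5. Could the lower-dose arm trigger alone?** For the two-of-six criterion with per-patient risk p, P(at least 2 of 6) = 1 − (1 − p)^6 − 6p(1 − p)^5. The risks below are assumed, and arms are treated as independent and complete.
- p = 0.10: 0.114
- p = 0.20: 0.345
- p = 0.30: 0.580

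Lower arm meets it and higher arm does not:
- risks 0.10 and 0.20: 0.114 × (1 − 0.345) = 0.075
- risks 0.20 and 0.30: 0.345 × (1 − 0.580) = 0.145

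So the order of events is plausible even when the higher dose is the riskier one.

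**6. Doses in a review window (illustration only).** Count a patient's nominal dosing days falling after the trigger and within an assumed 7, 14 or 21 days. Section 4.1.3 gives no length; 21 days is borrowed from 6.6 as an outer value, although under 6.6 nobody is dosed.

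| Assumed schedule | Maximum doses in 7 / 14 / 21 days |
|---|---|
| Weekly (Days 1, 8, 15, 22, 29) | 1 / 2 / 3 of five |
| Every 2 weeks (Days 1, 15, 29) | 1 / 1 / 2 of three |
| Every 4 weeks (Days 1, 29) | 1 / 1 / 1 of two |

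The minimum is 0 in every case. The same count is the possible exposure now and the possible delay under the fix.

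**The case against.** The strongest reply is that the unprotected interval is short. Confirmed liver events closely matching the stopping criteria are non-serious adverse events of special interest, reportable within 24 hours (8.3.6; Appendix 2, Section 5), and the Investigator gives a yes/no causality opinion for each event (Appendix 2, Section 3.2). If that opinion is yes and the event is unacceptable, 6.6 stops all dosing without joint review. What remains is mainly the case where the Investigator has not attributed the event, and there an automatic second pause is hardest to justify. This stands as a limit on size. It does not close the gap: no section sets an explicit deadline for the causality opinion, and 4.1.3 requires its own pause precisely because relation is unsettled.

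Second, one patient with a 3-fold rise and fatigue or nausea could interrupt a second arm, possibly because of an immune flare. That is a real cost. Leaving the decision to joint judgement is a defensible choice, but 4.1.3 has already chosen an automatic pause for the triggering arm, and it is hard to see why a higher dose should be treated more leniently.

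Third, redacted text follows the description of Arms 1 and 2, so dose spacing or staggering cannot be seen. This limits the importance that can be claimed; the 4.1.3 pause sentence itself is readable.

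A reader might also infer that 4.1.3 and 6.6 conflict. The documents do not show this. They have different triggers, and 6.6 is plainly the wider action. They do not cite each other (6.6 cites 4.1.2; 4.1.3 cites 7.1), but that is an editorial matter and not a separate defect.

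**Conclusion.** The point holds in a narrow form. With the lower-dose arm triggering, the mandatory text leaves the open higher-dose arm dosing while relatedness is assessed, unless the Investigator's 6.6 judgement or a discretionary stop intervenes. It would be too strong to say that the plan has no means of stopping that arm. Besides the routes above, pre-dose chemistry (Table 3), real-time data analysis (4.1.2) and unblinded Sponsor staff (6.3.2) remain, and a careful sponsor would probably use them. The dose cap helps less than it seems, since it comes from single doses in healthy participants.

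No number of extra doses can be stated as a finding: the regimen is redacted and the review length is not given. The counts and probabilities above rest entirely on assumed inputs. The conclusion assumes only that the two dosing levels in 4.2 are those of Arms 1 and 2; which arm is higher is not visible. This is a cheap improvement to a stopping rule, held with medium confidence.

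**What to change.** In the Part 2 liver pause sentence of 4.1.3, add: *Dosing is also paused in any concurrently open arm whose planned dose level or total exposure is higher than that of the triggering arm, until the Sponsor/Investigator review is complete.* Add the same action to the Part 2 non-liver rule, for an event that is not apparently unrelated.

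State two limits alongside it:
- Lower-dose arms, meaning those higher on neither measure, are not paused by this sentence and stay under 6.6 and joint discretion. Dosing frequency should not be a criterion by itself, because a lower-dose arm sharing the same frequency could then be caught.
- This safety pause is not a temporary interruption in the sense of 7.1.1.

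It would help to say whether a paused dose is given late or omitted. A cross-reference between 4.1.3 and 6.6 is a useful editorial addition.

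The cost is the added text, with no extra patients or procedures, and a dosing delay in the higher-dose arm for as long as the review lasts. That delay may disturb the arm's PK/PD profile, and one patient's flare could cause it. A prompt review keeps it small.
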